7.0 STATISTICAL ANALYSES & CONSIDERATIONS

7.1 Interim Analyses

Interim analyses will be conducted comparing unconfirmed Type 1 AMI in the principal discharge diagnosis position in the HEPLISAV-B and comparator vaccine groups using adjusted multivariable Cox proportional hazards models. The first interim analysis will take place after 41 events have occurred, which is anticipated within approximately 12 months after study start. An interim report is expected to be available to the FDA by 31 August 2019. A second interim analysis will be conducted after 68 events have occurred, anticipated to occur within 18 months after study start. A second interim report is expected to be available to the FDA by 29 February 2020.

Based on review of the interim results, the DMC may recommend completion of the study as planned. Alternatively, the DMC may recommend extension of the study. If the crude estimate of the hazard ratio (HR) based on un-adjudicated events is 2.5 or greater with a lower bound of the 95% confidence interval greater than 1, Dynavax will notify the FDA immediately with written follow-up as appropriate, and a formal comparison of confirmed AMIs will be conducted and reported to the DMC. The HR threshold of 2.5 was selected based on the level of increased risk we would have the power to detect.

At each interim analysis, a conditional power analysis will be performed using AMI events to estimate the power to reject a hazard ratio of 2.0 or greater on the final analysis, conditional on the data observed up to that point. Conditional power will be computed under three scenarios for the unobserved data: 1) that the observed event rates continue; 2) that future data will fit the null hypothesis of HR=2.0; and, 3) that future data will fit the hypothesis of HR=1.0. These estimates will provide a range for the likelihood that the study will definitively rule out a hazard ratio of 2.0 should it continue to completion under its original design.

A final analysis of unconfirmed Type 1 AMI events in the principal discharge diagnosis position will be conducted after the end of the 13-month follow-up for the last subject vaccinated, and a report is expected to be available to FDA by 30 September 2020. The exact timelines will depend on vaccine uptake and AMI event rates.

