This observational surveillance study will take place at Kaiser Permanente Southern California (KPSC), a large integrated health care organization serving approximately 4.4 million highly diverse members. KPSC has extensive experience in vaccine safety and effectiveness studies. In this non-randomized cluster design, HEPLISAV-B will be used exclusively at approximately 7 medical centers while another hepatitis B vaccine will be used exclusively at 8 other medical centers. Approximately 25,000 adult patients will receive HEPLISAV-B and approximately 25,000 adult patients will receive the comparator vaccine. Patients will be followed for occurrence of AMI through their electronic health records for 13 months.

The occurrence of AMI in patients who receive at least 1 dose of HEPLISAV-B will be compared with patients who receive at least 1 dose of the comparator hepatitis B vaccine. The number of vaccines administered and the number of suspected (unconfirmed) AMI will be

Dynavax Technologies Corporation HEPLISAV-B $^{\textcircled{B}}$

reported. Two interim comparisons of unconfirmed AMIs between vaccine groups will be conducted. The final analysis will be based on a Cox proportional hazards model employing inverse probability of treatment weighting (IPTW). Potential confounding factors with respect to cardiovascular disease risk factors in the use of the 2 vaccines will be adjusted for in data analyses. An independent data monitoring committee (DMC) will review interim and final analyses.

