4.4 Study Period

The study will begin with administration of the first dose of HEPLISAV-B and is contingent upon ACIP and RIPC recommendation of HEPLISAV-B. The study vaccination period will occur until 25,000 patients have received at least 1 dose of HEPLISAV-B, expected to take approximately 10.5 months based on historical vaccination trends. Each patient will be followed until the earliest of disenrollment from KPSC (not due to death and allowing for a 31-day gap in membership), death from any cause, or the end of the 13-month follow-up period after the index dose given during the vaccination period.

Table 4-1:Adult Hepatitis B Vaccine Recipients: Active Member at First Dose
Date, 2015 by Target (HEPLISAV-B) and Comparator Medical
Centers

	8 Comparator	7 Target	Total
	Medical Centers	Medical Centers	
N	47,964	45,766	93,730
Age (years)			
Mean (SD)	49.1 (10.83)	49.0 (10.90)	49.1 (10.86)
Sex	n (%)	n (%)	n (%)
Female	23,229 (48.43)	22,400 (48.94)	45,629 (48.68)
Male	24,735 (51.57)	23,366 (51.06)	48,101 (51.32)
Race/Ethnicity	n (%)	n (%)	n (%)
Asian	4043 (8.43)	5810 (12.7)	9853 (10.51)
Black	4027 (8.4)	4742 (10.36)	8769 (9.36)
Multiple	242 (0.5)	190 (0.42)	432 (0.46)
Native Am/Alaskan	152 (0.32)	127 (0.28)	279 (0.3)
Others	340 (0.71)	432 (0.94)	772 (0.82)
Pacific Islander	728 (1.52)	691 (1.51)	1419 (1.51)
Unknown	1107 (2.31)	829 (1.81)	1936 (2.07)
White	14,482 (30.19)	7914 (17.29)	22,396 (23.89)
Hispanic	22,843 (47.63)	25,031 (54.69)	47,874 (51.08)
Had type 2 diabetes history prior to the first dose	n (%)	n (%)	n (%)
No	9851 (20.54)	10,094 (22.06)	19,945 (21.28)
Yes	38,113 (79.46)	35,672 (77.94)	73,785 (78.72)
Had AMI history between 01/01/2010 to first dose date	n (%)	n (%)	n (%)
No	47,359 (98.74)	45,260 (98.89)	92,619 (98.81)
Yes	605 (1.26)	506 (1.11)	1111 (1.19)
Had hospitalized AMI in 12 months after first dose date	n (%)	n (%)	n (%)
No	47,891 (99.85)	45,713 (99.88)	93,604 (99.87)
Yes	73 (0.15)	53 (0.12)	126 (0.13)

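### The interim safety trigger reads only the crude hazard ratio, although the same section specifies an adjusted model and vaccine is assigned by non-randomized medical center

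*Protocol*

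**What the plan says.** Protocol Section 7.1 plans two interim comparisons of unconfirmed AMI, at 41 and 68 events, "in the HEPLISAV-B and comparator vaccine groups using adjusted multivariable Cox proportional hazards models". The next paragraph sets the only numerical action rule: "If the crude estimate of the hazard ratio (HR) based on un-adjudicated events is 2.5 or greater with a lower bound of the 95% confidence" (a limit that must exceed 1), then the sponsor notifies the FDA immediately, and a formal comparison of confirmed AMIs is made and reported to the DMC. The reason given for the level is: "The HR threshold of 2.5 was selected based on the level of increased risk we would have the power to detect". No reason is given for reading the crude estimate, and no parallel rule is set for the adjusted one. Section 7.7 speaks of covariates adjusting crude results, so crude means unadjusted here.

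Sections 4.2, 4.3 and 6.1 assign vaccine by medical center without randomization. The target centers are chosen for record-system clusters, proximity to the research headquarters and where the investigators work. Section 1.0 states the general intention: "Potential confounding factors with respect to cardiovascular disease risk factors in the use of the 2 vaccines will be adjusted for in data analyses".

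Section 4.3 describes the two groups of centers as alike in AMI risk, with modest race/ethnicity differences. In Table 4-1 the largest of these is the row "White 14,482 (30.19) 7914 (17.29) 22,396 (23.89"), with comparator centers first and target centers second. The same table shows hospitalized AMI within 12 months in 73 of 47,964 recipients at comparator centers and 53 of 45,766 at target centers.

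**The concern.** Exposure coincides with center group. The crude hazard ratio is therefore the vaccine effect multiplied by whatever baseline difference exists between the groups. If target-center patients have lower background risk, the crude estimate sits below the vaccine effect. The trigger can then stay silent when the adjusted estimate from the same look would have met the rule. The protocol treats adjustment as necessary for its other between-group comparisons, and only the urgent rule goes without it.

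At stake are two things: the immediate notification, and the formal comparison of confirmed AMIs ahead of the final analysis.

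**Working it through.** **Inputs.** Events at the looks: 41 and 68 (Section 7.1). Arms of about 25,000 each (Section 7.9), taken as equal person-time. One-sided alpha 0.025 (Table 7-1). 2015 AMI counts and race mix from Table 4-1.

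**1. The plan's own power figures.** With d events and 1:1 allocation, power = Φ(√d/2 × ln HR − 1.96).
- d = 41, HR 2.5: 0.835 (Table 7-1: 0.836).
- d = 41, HR 2.0: 0.602 (0.603).
- d = 68, HR 2.0: 0.815 (0.814).

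The figures reproduce. They are the power to reject HR = 1, not the chance that the trigger fires.

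**2. The trigger as an event split.** With x events in the HEPLISAV-B arm, crude HR = x/(d − x) and SE of its log = √(1/x + 1/(d − x)).
- d = 41: 29 vs 12 gives 2.42 and does not fire. 30 vs 11 gives 2.73 (lower limit 1.37) and fires.
- d = 68: 48 vs 20 gives 2.40 and does not fire. 49 vs 19 gives 2.58 (lower limit 1.52) and fires.

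The 2.5 point threshold is the binding condition at both looks.

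**3. Baseline difference in 2015.** (53/45,766)/(73/47,964) = 1.158/1.522 per 1,000 = 0.761. SE of the log = √(1/53 − 1/45,766 + 1/73 − 1/47,964) = 0.180, so the 95% CI is 0.53 to 1.08. If 0.761 persisted, a true HR of 2.5 would appear as 2.5 × 0.761 = 1.90. A true HR of 2.5/0.761 = 3.29 would be needed for a crude value of 2.5.

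**4. Chance that the trigger fires.** Given d, x is Binomial(d, p) with p = HR·b/(1 + HR·b), where b is the baseline ratio of target to comparator centers. At a true HR of 2.5:

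| b | 41 events | 68 events |
|---|---|---|
| 1.00 | 48% | 52% |
| 0.94 | 41% | 42% |
| 0.90 | 36% | 36% |
| 0.85 | 30% | 28% |
| 0.76 | 19% | 16% |

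At b = 0.76 more events do not help, because the crude estimate settles near 1.90. At a true HR of 3.0 and 41 events, the chance falls from 68% (b = 1) to 38% (b = 0.76).

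**5. What measured covariates might explain.** Race is the visible imbalance. If the AMI rate ratio of White to all other recipients is r (an assumption; the protocol gives no value), race alone implies b = (1 + 0.1729(r − 1))/(1 + 0.3019(r − 1)). This is 0.94, 0.90 and 0.84 for r = 1.5, 2 and 3. If the true baseline ratio is 0.761 and adjustment removes only a factor of 0.944, the residual is 0.761/0.944 = 0.806. An adjusted trigger would then fire 25% and 22% of the time at HR 2.5, a gain of about 5 to 6 points.

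**6. The opposite direction.** At a true HR of 1.0 and b = 1.32 (the inverse of 0.76), the crude trigger fires 2.4% of the time at 41 events and 0.7% at 68.

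**The case against.** **A crude trigger has real merits.** With 41 events, the twelve covariate groups of Section 6.3, and variable selection that is partly qualitative (Section 7.7), an adjusted estimate may be unstable and open to analyst choice. A crude ratio is quick and reproducible, which suits a screen on un-adjudicated events. This stands. It is a reason to keep the crude estimate and to fix the covariates in advance, but not to disregard the adjusted estimate.

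**The baseline difference is unproven.** The interval for 0.76 includes 1. It comes from one year, all 2015 recipients and a broader event definition than the interim endpoint. Mean age (49.1 vs 49.0 years, comparator first), male sex (51.6% vs 51.1%), diabetes (79.5% vs 77.9%) and prior AMI (1.26% vs 1.11%) were nearly balanced. This also stands, and it limits the size of the point.

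**Other safeguards exist.** A reader might infer that real harm would go unseen. The protocol does not support that. The DMC reviews the interim analyses (Section 6.5), which are the adjusted models, and may recommend extension. Interim reports go to the FDA after both looks, and the final analysis is weighted and uses confirmed events.

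**The trigger is not blind to the vaccine.** A reader might also infer that it measures center differences instead of a vaccine effect. It measures the product of the two.

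**Conclusion.** The mismatch is explicit within Section 7.1 and does not depend on any particular baseline ratio: the rule reads a confounded estimate and ignores the adjusted one produced at the same look. The size is uncertain. For baseline ratios of 0.94 to 0.85, the chance of firing at a true HR of 2.5 falls by 7 to 18 points at 41 events (48% to 41% or 30%) and by 10 to 24 at 68 (52% to 42% or 28%). The falls of 29 points (48% to 19%) and 36 points (52% to 16%) at 0.76 should not be read as the expected loss. They are the most that adjustment could recover at the 2015 point estimate, and only if measured covariates explain all of it with no loss of precision.

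A reader might expect frequent false alarms if the imbalance ran the other way, but step 6 shows they would be rare. Firing at a true HR of 2.0 is no false alarm either, since Section 7.3 sets out to exclude HR of 2.0 or more.

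Separately, the 2.5 point threshold gives only about an even chance of firing at HR 2.5 even without confounding. Adjustment does not change that.

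Conclusion: a cheap improvement to an expedited alarm, not a defect in the final inference.

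**What to change.** In Section 7.1, replace *the crude estimate of the hazard ratio* with *the crude or the adjusted estimate of the hazard ratio (from the interim multivariable Cox model, with a covariate set fixed before the first interim)*, and report both estimates to the DMC. Every result that fires under the present rule would still fire, so sensitivity cannot fall.

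The cost is one sentence and an early decision on covariates; the adjusted model is already planned at each look. The chance of an unneeded notification rises somewhat. By how much was not calculated, as it depends on how closely the two estimates agree. The change does not remove false alarms from the crude estimate. If the sponsor prefers the crude estimate alone, Section 7.1 should say why.

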7.9 Power Analyses

Approximately 50,000 patients (HEPLISAV-B: 25,000; another hepatitis B vaccine: approximately 25,000) will be included in the study and the accrual is assumed to be uniform during a period of approximately 10.5 months. Each patient will be followed for up to 13 months after their first dose of HEPLISAV-B or comparator vaccine administered during the study vaccination period. A 10% loss to follow-up during the study with a uniform loss rate is assumed. Assuming no difference in the risk of AMI between the two groups, we anticipate approximately 41 events at 12 months, 68 events at 18 months, and 78 events at the end of study if the event rate is 1.5/1000 person-years. In the first interim analysis, the study will have approximately 83% power to detect a hazard ratio \geq 2.5 and 60% power to detect a HR \geq 2.0, and in the second interim analysis the study will have 81% power to detect a HR \geq 2.0. In the final analysis, the study will have approximately 87% power to exclude HR \geq 2.0. The anticipated number of events based on other event rates and the power for a non-inferiority test based on other non-inferiority margins for the final analysis is presented in Table 7-1.

Time, Months	Event rate per 1000 person- years	# Events	Power, HR = 2.0 alpha = 0.025	Power, HR = 2.5 alpha = 0.025	Power, HR = 3.0 alpha = 0.025	Power, HR = 3.5 alpha = 0.025	Power, HR = 4.0 alpha = 0.025
9	1.0	16	0.277	0.44	0.583	0.696	0.782
	1.5	23	0.388	0.601	0.757	0.858	0.918
	2.0	31	0.490	0.725	0.866	0.938	0.972
12	1.0	27	0.442	0.669	0.820	0.906	0.952
	1.5	41	0.603	0.836	0.941	0.980	0.994
	2.0	55	0.728	0.924	0.982	0.996	0.999
18	1.0	45	0.644	0.869	0.959	0.988	0.997
	1.5	68	0.814	0.965	0.995	0.999	1.000
	2.0	90	0.909	0.992	0.999	1.000	1.000
24	1.0	52	0.705	0.911	0.977	0.995	0.999
	1.5	78	0.865	0.982	0.998	1.000	1.000
	2.0	104	0.942	0.997	1.000	1.000	1.000

Table 7-1:	Power for a Non-inferiority Test to Reject a Hazard Ratio in a Cox
	Proportional Hazards Model

Assumptions:

- Final HEPLISAV-B medical centers will be the same 7 as initially planned or will result in the same number of vaccine recipients in each arm
- Only doses given in family practice and internal medicine will be included (90% of all adult hepatitis B vaccine doses)
- Essentially all doses in HEPLISAV-B medical centers in family practice and internal medicine will be HEPLISAV-B

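### The interim notification trigger uses 2.5 as a cut-off for the observed HR and justifies it by power; at a true HR of 2.5 it fires only about half the time at each look.

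*Protocol*

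**What the plan says.** Section 7.1 plans two interim comparisons of unconfirmed Type 1 AMI: "The first interim analysis will take place after 41 events have occurred" and "A second interim analysis will be conducted after 68 events have occurred". The comparisons are to be made "using adjusted multivariable Cox proportional hazards models".

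The same section then sets a rule on the unadjusted estimate: "If the crude estimate of the hazard ratio (HR) based on un-adjudicated events is 2.5 or greater with a lower bound", which continues "with a lower bound of the 95% confidence interval greater than 1". If both parts are met, the sponsor notifies the FDA at once, and confirmed AMIs are formally compared and reported to the DMC. The reason given for the cut-off is: "The HR threshold of 2.5 was selected based on the level of increased risk we would have the power to detect".

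That power is in Section 7.9. At the first interim "the study will have approximately 83% power to detect a hazard ratio" of 2.5 or more, and 60% for 2.0 or more; at the second it is 81% for 2.0 or more. These agree with the one-sided 0.025 entries in Table 7-1. The protocol gives no firing probability for the two-part rule.

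**The concern.** The power to detect a true HR of 2.5 is the chance that a test rejects HR 1 when the truth is 2.5. It does not require the estimate to reach 2.5. Section 7.1 does require that, and cites the power as the reason. A rule that fires only when the estimate is at or above the true value fires about half the time, however many events there are.

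Someone reading Sections 7.1 and 7.9 together would take a silent trigger at 41 events as fairly strong evidence against an HR of 2.5, since 83% power is quoted. Under the rule as written it is weak evidence. At HR 2.0, the value the final analysis is designed to exclude, silence is the expected result at both looks.

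**Working it through.** **Inputs.** Looks at D = 41 and D = 68 events (Section 7.1). Allocation about 1:1: "HEPLISAV-B: 25,000; another hepatitis B vaccine: approximately 25,000" (Section 7.9). One-sided alpha 0.025 (Table 7-1). Trigger: estimate ≥ 2.5 and lower 95% limit > 1 (Section 7.1).

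**Step 1: reproduce the stated powers.** Schoenfeld's formula with 1:1 allocation is power = Φ(√D/2 × ln HR − 1.96).
- D = 41, HR 2.5: Φ(3.202 × 0.916 − 1.96) = 83.5%; stated 83% (table 0.836).
- D = 41, HR 2.0: Φ(3.202 × 0.693 − 1.96) = 60.2%; stated 60% (table 0.603).
- D = 68, HR 2.0: Φ(4.123 × 0.693 − 1.96) = 81.5%; stated 81% (table 0.814).

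All three reproduce. The formula's only condition is that the lower limit exceeds 1.

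**Step 2: which part of the trigger binds?** With equal person-time, X of the D events fall in the HEPLISAV-B group. The estimate is X/(D − X) and the lower limit is exp{ln[X/(D − X)] − 1.96 × √(1/X + 1/(D − X))}.

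| Events | First split with lower limit > 1 | First split with estimate ≥ 2.5 |
|---|---|---|
| 41 | 27:14 (HR 1.93, limit 1.01) | 30:11 (HR 2.73, limit 1.37) |
| 68 | 43:25 (HR 1.72, limit 1.05) | 49:19 (HR 2.58, limit 1.52) |

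The 2.5 condition binds at both looks. Whenever it is met, the confidence-limit condition is already met and adds nothing.

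**Step 3: firing probability.** X ~ Binomial(D, HR/(1 + HR)). The trigger fires if X ≥ 30 (D = 41) or X ≥ 49 (D = 68). The limit alone needs X ≥ 27 or X ≥ 43.

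| Events | True HR | Trigger as written | Lower limit alone | Stated in 7.9 |
|---|---|---|---|---|
| 41 | 2.5 | 48.0% | 83.3% | 83% |
| 41 | 2.0 | 23.9% | 61.5% | 60% |
| 68 | 2.5 | 51.5% | 94.6% | – |
| 68 | 2.0 | 20.9% | 76.9% | 81% |

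**Step 4: check by normal approximation.** P(fire) = 1 − Φ[(ln 2.5 − ln HR) × √D/2]. This gives 50% at HR 2.5 for any D. At HR 2.0, where ln 2.5 − ln 2.0 = 0.223, it gives 1 − Φ(0.714) = 23.8% at 41 events and 1 − Φ(0.920) = 17.9% at 68. The second-look figure at HR 2.0 is therefore 18–21% depending on method.

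**Step 5: both looks together.** The second look adds 27 events to the first 41. The chance that the trigger fires at either look is 61% at HR 2.5 and about 30% at HR 2.0.

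**Step 6: the HR that the rule does detect.** By the normal approximation, an 80% chance of firing at one look needs a true HR of 2.5 × exp(0.842 × 2/√D), which is about 3.25 at 41 events and 3.07 at 68.

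**Step 7: false triggers under HR 1, either look.** As written, about 0.2%. With the lower limit alone, about 3.9%.

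**The case against.** Four points can be made for the plan.

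- **The powers are right.** Section 7.9 describes the interim analyses, not the trigger, and its figures reproduce. A reader might infer an arithmetic error there, or a claim that the trigger is 83% sensitive. The protocol supports neither. This point stands. What remains is the sentence in 7.1 that rests the cut-off on a power which the two-part rule does not have.
- **The trigger is not the only safeguard.** A reader might infer that a silent trigger keeps a signal from the FDA. It does not. Section 7.1 schedules interim reports to the FDA whatever the HR, and the DMC reviews both interim analyses, which use adjusted models and carry conditional power against HR 2.0. This stands and limits the consequence to two things: how quickly the FDA is told, and whether confirmed events are compared early.
- **A high bar limits false alarms.** Pairing an effect-size floor with a confidence limit is a legitimate choice on un-adjudicated events. That stands too, but it is not the reason the protocol gives.
- **A crude HR suits a quick first flag.** A reader might go further and infer that it is biased downward, because Table 4-1 shows 53/45,766 against 73/47,964 AMIs in 2015, a ratio of 0.76. The 95% interval is about 0.53 to 1.08 and includes 1, and the table counts hospitalized AMI rather than the principal-position interim endpoint. It is not evidence of bias. Nor do the documents show that the adjusted Cox model planned for the interims is inadequate, so there is no case here for requiring IPTW at that stage.

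**Conclusion.** The rationale for the 2.5 cut-off is wrong as written. The study has about 83% power at 41 events to put the lower limit above 1 when the true HR is 2.5. The trigger has about a 48% chance of firing in that case, and about 24% at HR 2.0. Per look, the second interim is no better at HR 2.0 (18–21%); the cumulative chance does rise, to about 30%.

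The figures assume equal person-time in the two groups, no clustering, and no misclassification of un-adjudicated events. Non-differential misclassification would lower the firing rates further. The main result, roughly 50% at the threshold value, does not depend on the method.

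This is a should-fix. The sample size, the primary analysis and its error rate do not change, and the trigger is not a stopping rule. But it is the pre-set numeric rule for urgent action on the study's central safety question, and the protocol should describe its behaviour correctly.

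**What to change.** **Needed.** In Section 7.1, delete or correct the sentence that justifies 2.5 by power. In 7.1 or 7.9, state the trigger's own firing probabilities, separately from the power of the confidence-limit test: about 48% (HR 2.5) and 24% (HR 2.0) at 41 events, 52% and 18–21% at 68 events, 61% and 30% at either look, and about 0.2% under HR 1. If the floor is kept to avoid false alarms, say so. The cost is wording only.

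**Optional.** If the sponsor wants sensitivity near the stated 83%, 60% and 81%, trigger on the lower 95% limit above 1 alone. The exact figures are then 83%, 62% and 77%. The price is a rise in false triggers under HR 1 over both looks from about 0.2% to about 4%, each leading to a notification and an earlier confirmed-event comparison. Statisticians may differ on that trade.

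The adjusted Cox estimate already planned for the interims could be reported beside the crude HR whenever the trigger is assessed, with no new analysis.
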